7.5. Follow up at 6 months

The following activities will take place at the respective research laboratory. This visit will take approximately three hours with no overnight admission. Technical work in this phase will be performed by Ministry of Health personnel (Vector Control Division).

- **Admission** weight, height, clinical history
- **Stool** collection for:
 - Calprotectin and fecal occult blood (performed on site).
- **Urine** collection and storage for future processing of CAA. This will allow for monitoring of re-infection in the cohort.
- **PZQ or Placebo** administration at the study assigned dose after a meal consisting of local foods and monitoring for AE post-treatment

- **Blood:** Five ml for morbidity studies including CBC, iron biomarkers, EED biomarkers, pro-inflammatory cytokines and further 7 ml from the sub-group of N=150 children who were selected at baseline for immunology assays (such as flow cytometry, Luminex, ELISpot and ELISA). Before discharge, another blood sample will be removed between 6 – hours after administration of the first dose of the study drug. This enables monitoring for possible toxicity.
- **Ultrasound** to determine possible changes in baseline morbidity patterns

7.6. Follow-up and close out at 12 months

The following activities will take place at the respective research laboratories. This visit will take approximately 5-6 hours with no overnight admission. Technical work in this phase will be performed by Ministry of Health personnel (Vector Control Division).

- Weight, height, clinical history
- Lactulose/Mannitol beverage. They will take 2ml/kg of lactulose-mannitol solution (containing 250 mg/mL lactulose and 50 mg/mL mannitol in purified water, in aliquots of 20ml) up to a maximum of 20 ml. Urine will be collected for 2 hours after ingestion of the solution. 2ml aliquots of each of the urine samples will be collected and stored between 2 – 8°C for lactulose-mannitol assay.
- **Urine** test for CAA/CCA assay
- **Stool** collection for:
 - Calprotectin and fecal occult blood (performed on site).
 - Kato Katz (two samples in Uganda and three in Philippines) with some collected prior to visit
- **Urine** collection for CCA and CAA
- **Blood:** Five ml for morbidity studies including CBC, iron biomarkers, EED biomarkers, pro-inflammatory cytokines and further 7 ml from the sub-group of N=150 children who were selected at baseline for immunology assays (such as flow cytometry, Luminex, ELISpot and ELISA).
- **PZQ** administration at the study assigned dose after a meal consisting of local foods for children infected with schistosomiasis based on Kato-Katz or urine CCA
- **Albendazole** administration for any child infected with soil-transmitted helminths

- **Ultrasound** to determine persistence of morbidity

7.7. Final Study Visit

This visit will occur with the 12 month follow up visit as above. Technical work in this phase will be performed by Ministry of Health personnel (Vector Control Division). All children will be treated for schistosomiasis as per Uganda DOH and WHO recommendations.

7.8. Monitoring PZQ resistance

Stool samples will be obtained at all visits from a sub-sample of the participants to do PZQ resistance testing. Briefly, eggs from participant's stool will be hatched and individual miracidia will be picked up using a micropipette under a microscope and transferred onto Whatman FTA[®] indicator cards. The Whatman FTA[®] cards will be allowed to dry in the shade for one hour. Up to 100 miracidia should be collected per participant, dependent on the intensity of infection.²⁴

7.9. Early Termination Visit (if needed)

A participant may, at any time point, voluntarily withdraw from the study based on their personal judgement. In the event that this arises, efforts will be made to understand the reasons for the participant's decision. If the concerns are within the means of the study team to manage, proper attention will be given with the aim of maintaining participation to completion.

7.10. Early Termination Visit (if needed) Unscheduled Visit (if needed) Early Termination Visit (if needed) Unscheduled Visit (if needed) Early Termination Visit (if needed) Unscheduled Visit (if needed)

Participants may visit the research center or contact the research team at any time outside the stipulated scheduled visits. This may be due to concerns regarding safety.

8. STUDY PROCEDURES/EVALUATIONS

8.1. Clinical Evaluations

- Medical history
- Medications history
- Physical examination height and weight.
- Abdominal ultrasound of liver and spleen

8.2. Laboratory Evaluations

8.2.1. Clinical Laboratory Evaluations

We will obtain the following:

- Hematology: hemoglobin, hematocrit, white blood cells (WBC) with differential count, platelet count.
- Renal and liver function tests
- Urinalysis: dipstick urinalysis, including protein, hemoglobin and glucose; if dipstick is abnormal, complete urinalysis with microscopic is required.
- Stool assay: Kato-Katz, Calprotectin, Fecal Occult Blood
- CCA/CAA-urine based point of care antigen tests for schistosomiasis

8.2.2. Special Assays or Procedures

- Lactulose:Mannitol assays
- Calprotectin Stool
- Fecal occult blood
- Alpha-1 antitrypsin
- Endocab antibody
- Myeloperoxidase
- Neopterin

- Pharmacokinetic assays from serum
- Immunologic assays using cells, whole blood and plasma

8.2.3. Specimen Preparation, Handling, and Shipping

Samples will be spun down with centrifuge. The CBC will be run and serum will be placed in three aliquots at each site. The aliquots will be stored in -80 freezer until shipment. Every six months, two aliquots will be shipped from the field laboratories to MRC in Entebbe and RITM in Manilla. From there, one aliquot will be stored in -80 and the other shipped to Rhode Island Hospital for multi-plexed assays (markers of EED and iron status).

8.2.3.1. Instructions for Specimen Preparation, Handling, and Storage

8.2.3.2. Specimen Shipment

Samples will be transported from Lake Albert to Entebbe UVRI by road and stored there at -80 C and from Leyte to Manilla by air until further shipment to the United States (serum aliquot and urine for lactulose-Mannitol) and to Liverpool (serum for Pharmacokinetics). International shipment will be done by World Courier which has extensive experience in the transport of biologic specimens.

9. ASSESSMENT OF SAFETY

9.1. Specification of Safety Parameters

Safety will be assessed by the frequency and severity of actively monitored and passively captured adverse events continuously in the 12 hours after every investigational product administration given throughout the duration of the trial. Parent reported adverse events during that time period will also be captured. This is made possible due to the continuous onsite presence of the trial doctor. The 12 hour duration is deemed sufficient monitoring since praziquantel is a moderately fast acting drug with elimination in less than 24 hours.

9.2. Methods and Timing for Assessing, Recording, and Analyzing Safety Parameters

9.2.1. Adverse Events

Adverse Event:

ICH E6 defines an AE as any untoward medical occurrence in a patient or clinical investigation subject administered a pharmaceutical product regardless of its causal relationship to the study treatment. FDA defines an AE as any untoward medical occurrence associated with the use of a drug in humans, whether or not considered drug related.

An AE can therefore be any unfavourable and unintended sign (including an abnormal laboratory finding), symptom, or disease temporally associated with the use of medicinal (investigational) product. The occurrence of an AE may come to the attention of study personnel during study visits and interviews of a study recipient presenting for medical care, or upon review by a study monitor.

AEs, including solicited local (injection site) and systemic (subjective and quantitative) reactions, will be captured on the appropriate data collection form and eCRF. Information to be collected for unsolicited non-serious AEs includes event description, date of onset, assessment of severity, relationship to study product and alternate etiology (assessed only by those with the training and authority to make a diagnosis, date of resolution, seriousness and outcome. AEs occurring during the trial collection and reporting period will be documented appropriately regardless of relationship. AEs will be followed through resolution.

Any medical condition that is present at the time that the subject is screened will be considered as baseline and not reported as an AE. However, if the severity of any pre-existing medical condition increases, it should be recorded as an AE.

All AEs must be graded for severity and relationship to study product (see definitions). Adverse events characterized as intermittent require documentation of onset and duration of each episode. The start and stop date of each reported AE will be recorded on the appropriate data collection form and eCRF.

Severity of Event:

AEs will be assessed by the investigator using a protocol-defined grading system (toxicity table included as an appendix). For events not included in the protocol-defined grading system, the following guidelines will be used to quantify severity:

- Mild (Grade 1): Events require minimal or no treatment and do not interfere with the subject's daily activities.
- Moderate (Grade 2): Events result in a low level of inconvenience or concern with therapeutic measures. Moderate events may cause some interference with functioning and daily activities.
- Severe (Grade 3): Events interrupt the subject's daily activities and may require systemic drug therapy or other treatment. Severe events are usually incapacitating.

Changes in the severity of an AE should be documented to allow an assessment of the duration of the event at each level of intensity to be performed. Adverse events characterized as intermittent require documentation of onset and duration of each episode.

Relationship to Study Products: The assessment of the relationship of an AE to the administration of study product is made only by those with the training and authority to make a diagnosis based on all available information at the time of the completion of the eCRF. Whether the AE is related or not, is not a factor in determining what is or is not reported in this trial. If there is any doubt as to whether a clinical observation is an AE, the event should be reported.

In a clinical trial, the study product must always be suspect. To help assess, the following guidelines are used.

- **Related** – There is a reasonable possibility that the study product caused the adverse event. Reasonable possibility means that there is evidence to suggest a causal relationship between the study product and the adverse event.
- **Not Related** – There is not a reasonable possibility that the administration of the study product caused the event.

9.2.2. Serious Adverse Events

Serious Adverse Event (SAE):

An adverse event or suspected adverse reaction is considered “serious” if, in the view of either the investigator or sponsor, it results in any of the following outcomes:

- Death,
- a life-threatening adverse event¹,
- inpatient hospitalization or prolongation of existing hospitalization,
- a persistent or significant incapacity or substantial disruption of the ability to conduct normal life functions, or
- Important medical events that may not result in death, be life-threatening, or require hospitalizations may be considered serious when, based upon appropriate medical judgment they may jeopardize the patient or subject and may require medical or surgical intervention to prevent one of the outcomes listed in this definition. Examples of such medical events include allergic bronchospasm requiring intensive treatment in an emergency room or at home, blood dyscrasias or convulsions that do not result in inpatient hospitalization, or the development of drug dependency or drug abuse.

¹ Life-threatening adverse event. An adverse event is considered “life-threatening” if, in the view of either the site principal investigator or sponsor, its occurrence places the patient or subject at immediate risk of death. It does not include an adverse event, had it occurred in a more severe form, might have caused death.

SAEs will be:

- Assessed for severity and relationship to study product and alternate etiology.

- Recorded on the appropriate SAE data collection form and eCRF.
- Followed through resolution.
- Reviewed and evaluated by an Independent Safety Monitor (ISM) (as deemed necessary), the DSMB (periodic review unless related), and the IRB.

9.2.3. Procedures to be Followed in the Event of Abnormal Laboratory Test Values or Abnormal Clinical Findings

Children who are noted to have an acute or chronic medical condition at enrolment or follow up will be referred for appropriate treatment if the issue cannot be managed by the study paediatrician. This may include referral for severe undernutrition or chronic disease such as asthma. For any child found to be anemic (hgb < 11.0 g/dL) we will provide iron supplements.

9.3. Reporting Procedures

9.3.1. Serious Adverse Events

SAEs will be followed until resolution even if this extends beyond the study-reporting period. Resolution of an SAE is defined as the return to pre-treatment status or stabilization of the condition with the expectation that it will remain chronic.

Any AE that meets a protocol-defined serious criterion must be submitted immediately (within 24 hours of site awareness) on an SAE form to both study Principal Investigators, the study clinical officer, and the independent safety monitor described below.

SAE Email Address: [contact] and [contact]

In addition to the SAE form, select SAE data fields must also be entered into the electronic data capture system. Please see the protocol-specific MOP for details regarding this procedure.

Other supporting documentation of the event may be requested by the DSMB and should be provided as soon as possible.

9.3.2. Reporting of Pregnancy

Not applicable

9.4. Type and Duration of Follow-up of Subjects after Adverse Events

For subjects who are excluded based on chronic or acute medical condition or undernutrition, we will ensure follow up was secured at the community health center. The study field workers will re-visit the homes of these families to ensure follow up occurred.

For children found to have mild or moderate anemia, we will provide a 2-month supply of iron (mild) or 4 month supply (moderate) and we will recheck CBC at 6 month visit and repeat this approach based on laboratory findings.

We expect that adverse events related to drug dosing will resolve prior to discharge at 12 hours (enrollment) or 3-4 hours after dose (6 month visits).

9.5. Halting Rules

Safety findings that would lead to temporary suspension of enrolment include:

- 1) A greater than expected number of total serious adverse events deemed associated with the study product as defined by two or more SAEs associated with the study product among the first 20 children enrolled and then five or more serious adverse events among children, associated with the intervention per 100 children enrolled (5%).
- 2) 15 subjects per 100 enrolled experiencing adverse drug events as defined by a) an unexpected adverse event, as defined by a clinical adverse event (not a laboratory defined adverse event) that is not listed as expected with treatment, that occurs within 2 days after dosing, If the total number of unexpected adverse drug events occurs among 15 children per 100 enrolled or 15% or more of children, halting rules would apply.

If either of the above occurs, this would lead to temporary suspension of enrolment and a safety review (either routine or ad hoc), the objective of which is a decision as to whether the study (or intervention for an individual or study cohort) should continue per protocol, proceed with caution, be further investigated, be discontinued, or be modified and then proceed. Suspension of enrollment (for a particular group or for the entire study) is another potential outcome of a safety review.

Subsequent review of serious, unexpected, and related AEs by the Medical Monitor, DSMB, IEC/IRB, the sponsor(s), or relevant local regulatory authorities may also result in suspension of further trial interventions/administration of study product at a site. The study sponsor(s) retain the authority to suspend additional enrollment and study interventions/administration of study product for the entire study, as applicable.

Individual Halting Rules

A child will be discontinued from the study if he/she experiences a severe allergic/anaphylactic reaction to any dose of Praziquantel given during the study (enrolment or six months).

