| Description of Study Design: | 
 1. Drug efficacy assessed by novel antigenic endpoints (CCA and CAA) among all children, and in relation to PK/PD parameters associated with cure (Area-Under-the Curve (AUC)) at 4 +/- 1 weeks post-PZQ in a subset of children. 2. 12 hour clinical monitoring for safety including active capture of adverse events and assessment of toxicity through serum chemistries and hematologic parameters. 3. Iron status, hemoglobin, and age and gender adjusted longitudinal growth and nutritional status 4. Biomarkers of inflammation and EE including fecal calprotectin, urine lactulose:mannitol ratio, serum endotoxin, serum endotoxin core antibody, and proinflammatory cytokines 5. Inter-individual variability in PZQ AUC as modified by Environmental Enteric Dysfunction (EED) 6. Immune responses to S. mansoni infection and treatment 7. Prevalence and the pattern of schistosomiasis-related morbidity as determined by ultrasound scan. 
Four parallel arm randomized quasi-double blinded placebo-controlled trial with a 4 week, 6 months and 12 month follow up. Interventions will be given at baseline and at 6 months. Parasitological endpoints will be measured at 4 weeks. Morbidity endpoints will be measured at 6 and 12 months.
 |
| Estimated Time to Complete Enrolment: | 24 months |

Table 1: Treatment Arms*

| | Number of subjects | Baseline Dose | 6 months post baseline dose |
|-------|--------------------|---|---|
| ARM 1 | 150 | 40 mg/kg dose PZQ (40 mg/kg followed by Placebo 3 hours later) | Placebo followed by Placebo 3 hours later |
| ARM 2 | 150 | 40 mg/kg dose PZQ (40 mg/kg followed by Placebo 3 hours later) | 40 mg/kg dose (40 mg/kg followed by Placebo 3 hours later) |
| ARM 3 | 150 | 80 mg/kg split dose PZQ (40 mg/kg followed by 40 mg/kg 3 hours later) | Placebo followed by Placebo 3 hours later |
| ARM 4 | 150 | 80 mg/kg split dose PZQ (40 mg/kg followed by 40 mg/kg 3 hours later) | 80 mg/kg split dose (40 mg/kg followed by 40 mg/kg 3 hours later) |

*** These numbers represent subject totals across both sites. At each site, approximately N=75 subjects will be enrolled in each of the 4 arms providing N=300 subjects at each site.**

Figure 1: Schematic of Study design

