2.3. Potential Risks and Benefits

2.3.1. Potential Risks

PZQ is safe in preschool children as evidenced by a large number of published studies. The investigators, however, recognize that the study population constitutes a vulnerable population of very young children. This vulnerable population is studied because the objectives are to understand the safety and efficacy of praziquantel, a drug that benefits people globally, in very young children. Currently, these children are not included in preventive chemotherapy campaigns due to lack of data with respect to optimal dosing, PK/PD, safety at varying doses, and efficacy. The two PIs for the planned trial are both pediatricians with significant experience leading pediatric studies of helminthiasis in LMICs.

The primary risk is exposure to a higher dose of praziquantel than is routinely given. This is necessary and informed by a study conducted by co-PI [name] that demonstrated that standard 40 mg/kg dosing in young children is likely too low given lower cure rates in this age group and that 80 mg/kg is the necessary dose based on modelling. Children experienced minimal side effects in that study at 60 mg/kg. Further, a 60 mg/kg dose has been routinely given for *S. japonicum* to children over the age of four. Finally, a study addressing treatment for *S. mekongi* employed a dose of 75 mg/kg (split 50/25 mg/kg over 4 hours) for children aged 10-15 years.¹¹

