Three events were denoted “severe” (vomiting (2) and vertigo) in the 75 mg/kg dose group which had N = 45 children; no Serious Adverse Events as defined by death, life threatening event, need for hospitalization, or persistent morbidity/incapacity, were reported in either group. The reported rates of adverse events were slightly higher in the 75 mg/kg group than the 40 mg/kg comparison group. In a separate recently published study in Cote D’Ivoire, escalating doses of praziquantel (20, 40, 60 mg/kg) were examined in a cohort of children including pre-school age children (PSAC) aged 2-6 years.¹² Among PSAC, adverse events were mild with fewer adverse events observed three hours post-treatment compared to pre-treatment. Importantly, the number of adverse events was similar among the three praziquantel treatment doses, with fewer adverse events observed in the placebo-treated groups. Only mild expected adverse events were reported with the exception of one moderate grade adverse event 3 hours after the first praziquantel dose in one PSAC (diarrhea). No serious adverse events were noted at any dose. We will minimize risk by “admitting” children for observation with active and passive assessment for adverse events for 12 hours. We will also provide children with a meal to minimize side effects. **Finally, we will administer the 80 mg/kg dose as two doses of 40 mg/kg split over three hours.**

There is also a small risk to young children from blood draw, which is due to iron deficiency anemia as a blood draw removes red blood cells and iron. This risk is minimal given the small amount (7 – 12 ml) that will be drawn at each of three time points, representing 20 – 25 ml in a year. For the immunology study subpopulation, an extra blood draw of 7ml will be made at 4-week follow up time point. Very minimal risks are associated with venipuncture itself, which will be performed by trained medical personnel.

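### Both study-level halting counts in section 9.5 pool the two doses, so an excess of harm confined to 80 mg/kg forces a pause later or less surely

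*Combined protocol and SAP*

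**What the plan says.** Section 9.5 gives two study-level findings that suspend enrolment and start a safety review.

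- **Rule 1, related serious adverse events (SAEs).** An early limb of "two or more SAEs associated with the study product among the first 20 children enrolled", then "five or more serious adverse events among children, associated with the intervention per 100 children enrolled (5"%).
- **Rule 2, unexpected clinical adverse events within 2 days of dosing.** The limit is "15 children per 100 enrolled or 15% or more of children".

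Every denominator is all children enrolled, and neither rule names a dose. Dose enters 9.5 only after a rule has been met: "Suspension of enrollment (for a particular group or for the entire study) is another potential outcome of a safety review".

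Allocation to the two baseline doses is 1:1. The note to Table 1 in the Protocol Summary says "At each site, approximately N=75 subjects will be enrolled in each of the 4 arms", and two of the four arms start at each dose. Section 2.3.1 says "The primary risk is exposure to a higher dose of praziquantel than is routinely given".

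Other safeguards carry no count. SAEs are reported within 24 hours (9.3.1). The Medical Monitor and, where deemed necessary, the independent safety monitor review them in real time, and the DSMB may be shown data by arm (9.6.2). Formal harm rules are left for discussion with the DSMB (11.3.1), and its charter is not among the documents.

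**The concern.** The trial adds one new exposure, 80 mg/kg in children from 12 months of age, and the mandatory triggers are least sensitive to harm from it. Pooling averages the 80 mg/kg rate with that of a group receiving the currently recommended dose.

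Patient safety is at stake, in a limited sense: whether a pause is forced, and after how many children have been dosed at 80 mg/kg. This matters most for rule 2. The 24-hour reporting and real-time review are stated for SAEs, and nothing equivalent is stated for non-serious unexpected events. For those the pooled count is the only stated mandatory trigger. Otherwise detection rests on DSMB meetings at three months and then every six months (11.3.1, 15.4), and on discretion.

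**Working it through.** **Plan's own figures.** 5/100 = 5% and 15/100 = 15%, as stated. Section 9.5 gives no operating characteristics.

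**Inputs.** From the documents: the counts in 9.5 and 1:1 dosing, so about 50 of every 100 enrolled per dose and 10 of the first 20. All event rates are assumptions, shown as ranges. For related SAEs, 8% at 80 mg/kg is the high end. Section 2.3.1 describes 45 older children given 75 mg/kg and says "no Serious Adverse Events as defined by death, life threatening event, need for hospitalization, or persistent morbidity/incapacity, were reported in either group"; the exact 95% upper limit for 0 of 45 is 1 - 0.025^(1/45) = 0.079. The calculation covers baseline dosing only and allows at most one event per child.

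**Rate needed to reach the line.** With 1:1 dosing the pooled rate is (p80 + p40)/2, so p80 must reach twice the limit minus p40.

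- Rule 1: 2 × 5% - 0% = 10%, or 2 × 5% - 2% = 8%.
- Rule 2: 2 × 15% - 0% = 30%, or 2 × 15% - 5% = 25%.

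The proposed by-dose lines are 4/50 = 8% and 10/50 = 20%. With 2% at 40 mg/kg, the rule 1 line of 8% equals what pooling already requires, so little gain is expected there. For rule 2, 20% lies below 25-30%.

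**Rule 2 by 100 enrolled.** Exact binomial sums over 50 + 50 children. Pooled: total of 15 or more. With by-dose count: that, or 10 or more in either dose group.

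| 80 vs 40 mg/kg | Pooled | With by-dose count |
|---|---|---|
| 20% vs 0% | 0.061 | 0.556 |
| 20% vs 5% | 0.260 | 0.563 |
| 25% vs 0% | 0.252 | 0.836 |
| 25% vs 5% | 0.547 | 0.840 |
| 8% vs 8% (false pause) | 0.013 | 0.019 |

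**Rule 1 by 100 enrolled.** First 20 as 10 + 10, then 40 + 40. Pooled: 2 or more in the first 20, or a total of 5 or more. With by-dose count: that, or 4 or more of 50 in either group.

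| 80 vs 40 mg/kg | Pooled | With by-dose count |
|---|---|---|
| 8% vs 0% | 0.431 | 0.600 |
| 8% vs 2% | 0.614 | 0.676 |
| 6% vs 0% | 0.241 | 0.384 |
| 6% vs 2% | 0.432 | 0.485 |
| 4% vs 1% | 0.161 | 0.206 |
| 3% vs 1% | 0.095 | 0.118 |
| 2% vs 2% (false pause) | 0.096 | 0.105 |

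**Rule 1 over all 600.** The text allows two readings of the per-100 count.

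- *Running rate.* Simulated in blocks of 4 (block size assumed). Pooled: 2 or more by child 20, then at least 5 events and at least 5%. By-dose: at least 4 events and at least 8% within dose. At 8% vs 0-2%: about 0.60-0.87 pooled, 0.86-0.91 with the by-dose count. At 6% vs 0%: about 0.30 and 0.54. False pauses at 2% vs 2%: about 0.11 and 0.12.
- *Successive hundreds.* The first hundred includes the 2-in-20 limb and five more follow. At 8% vs 0%, pooled: 1 - (1 - 0.431)(1 - 0.371)^5 = 0.944, against 0.994 with the by-dose count. At 8% vs 2%: 0.994 and 0.998. At 6% vs 0%: 0.717 and 0.930. False pauses at 2% vs 2%: 0.303 and 0.348. At 8% the difference here is mainly delay.

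**The case against.** **Pooled triggers with by-arm DSMB review are a legitimate design.** This stands. The list in 9.5 is not worded as exhaustive. The Medical Monitor, DSMB, ethics committees or sponsor may suspend after review, and the DSMB chair may call an ad hoc meeting. A reader might infer that harm at 80 mg/kg would go unexamined. The documents do not support that, least of all for related SAEs. What remains is that none of these provisions fixes a point at which an excess at 80 mg/kg requires a pause.

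**A by-dose rule may already exist.** Section 9.6 says the DSMB sets criteria for ad hoc meetings and that its suggestions on the protocol have been incorporated. A rule that needs unblinding could reasonably sit in the charter. A reader might infer that the trial has no by-dose rule at all; the documents show only that none is stated in them.

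**The rates are high and the gain for SAEs is small.** Largely right. Section 2.3.1 reports no SAEs at 75 mg/kg in older children, nor at up to 60 mg/kg in preschool children. If 40 mg/kg is event-free, the by-dose count pauses at the fourth related SAE instead of the fifth. A reader might infer that it would make a pause almost certain across the 600. Read as a running rate with the proposed threshold, it does not. A line at 5% within dose would be a different rule with more false pauses, and is not proposed here.

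**An event-free 40 mg/kg group is a boundary case.** Correct: both groups receive the same first 40 mg/kg. The doubling of the required rate is therefore a maximum, and the ranges above include non-zero rates at 40 mg/kg.

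**Conclusion.** The point holds as a cheap improvement, not as an error in the plan. Both study-level counts pool the doses and no by-dose count is stated, so a mandatory pause for an excess confined to 80 mg/kg comes later or less surely.

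Rule 2 carries the point. At a true 25% against none at 40 mg/kg, the pooled count trips by 100 enrolled about one time in four, against 0.84 with the by-dose count, for a rise in false pauses of about 0.006 at 8% in both groups. For rule 1 the gain by 100 enrolled is 0.06 to 0.17 at an 8% rate that is itself the high end, and smaller at 3-4%; existing case-by-case review reduces what that gain is worth.

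The direction does not depend on the assumed rates, because an added count can only bring a pause forward. The size does. It also depends on how the per-100 wording is read and on what the charter contains.

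**What to change.** Keep both pooled counts and add to 9.5:

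*Each count is also evaluated within baseline dose group (40; 80 mg/kg): 4 or more related SAEs per 50 children enrolled in a dose group, or 10 or more children with unexpected clinical adverse events per 50. The unblinded trial statistician prepares this and reports it only to the DSMB, which confirms the thresholds.*

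If the charter already holds a by-dose rule, a cross-reference in 9.5 is enough.

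The preparer should be the trial statistician, whom 11.3.1 already unblinds for the interim analysis. The data coordinating center generates the halting reports (15.4) but also handles daily queries, data management and analysis, so it should stay blinded.

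The cost is one amendment to 9.5 with a matching charter entry, one extra unblinded tabulation of data already collected, and a few more temporary pauses. By 100 enrolled, false pauses rise from 0.096 to 0.105 for rule 1 (2% in both groups) and from 0.013 to 0.019 for rule 2 (8% in both). Over all 600, for rule 1 at 2% in both groups, they go from about 0.11 to 0.12 as a running check, or from 0.303 to 0.348 as successive hundreds.
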